6.13.4. Analyses to be Performed

A listing will be provided of all immunogenicity assessments for those patients who at any time had ADA Present. This includes the laboratory ADA assay result (Detected or Not Detected), LY concentration from a simultaneous PK sample, and the clinical interpretation result that combines these (ADA present, ADA Not Present, ADA Inconclusive, Missing). When Detected, a titer will be included, and TE ADA+ observations will be flagged. Also included will be the laboratory NAb assay result (Detected or Not Detected) and the NAb clinical interpretation result (NAb Present, NAb Not Present, NAb Inconclusive, Missing) when the NAb assay was performed (see [Table 6.5](#)).

For the remainder of this section, "ADA result" will refer to the clinical interpretation result. "NAb result" will be handled similarly.

The number and proportion of patients who are TE ADA+ will be tabulated by treatment group, where proportions are relative to the number of patients who are TE ADA evaluable, as defined above. The tabulation will include all postbaseline observations, the number and proportion of patients with ADA Present at baseline, and the number and proportion of TE ADA+ patients exhibiting NAb+.

For each TE ADA+ patient, a plot will be constructed of titer values from individual samples over time. Samples that are ADA Not Present are ADA Inconclusive will also be indicated.

A summary will be provided of the number and percentage of LY-treated patients experiencing specific TEAEs (see [Table 6.7](#)) by patient TE ADA status (TE ADA+, TE ADA-, TE ADA Inconclusive). The PT will be ordered by decreasing incidence in TE ADA+ status group. For event terms not occurring in any TE ADA+ or TE ADA Inconclusive patient, a summary will be provided of the number of distinct terms reported, but individual PTs will not be summarized.

A listing will be provided of all TEAEs alongside ADA data, for any patient who had ADA Present at any time (including baseline) or had any specific TEAE (see [Table 6.7](#)). This listing includes a time course of ADA (clinical interpretation result plus flags for samples meeting TE ADA+ criteria and for NAb+ samples) along with the TEAE.

Table 6.7. TEAE for Analysis with ADA / NAb Results

Events satisfying Anaphylaxis SMQ (narrow or broad)
Events satisfying Hypersensitivity SMQ (narrow or broad)
Events satisfying Angioedema SMQ (narrow or broad)
Events mapping to High Level Term (HLT) of Injection site reaction
Events mapping to High Level Term (HLT) of Administration site reaction

Abbreviations: ADA = anti-drug antibody; HLT = high level term; NAb = neutralizing antibody; SMQ = standardized Medical Dictionary for Regulatory Activities (MedDRA) query.

6.14. Histopathology

Biopsies will not be summarized for this study.

6.15. Subgroup Analyses

The following subgroups will be analyzed:

- Demographic subgroups:
 - Gender: M, F
 - Age group: <65 years, ≥65 years
 - Weight category:
 - <80 kg, ≥80 kg
 - <100 kg, ≥100 kg
 - Body mass index (BMI) category: underweight (<18.5 kg/m²); normal (≥18.5 and <25 kg/m²); overweight (≥25 and <30 kg/m²); obese (≥30 and <40 kg/m²); extreme obese (≥40 kg/m²)
- Geographic region subgroups: United States (US); Other (Non-US): Canada, Germany, Japan, Poland
- Baseline severity subgroups:
 - Baseline sPGA category: 3, 4, 5
 - Baseline sPGA category: 3, combined 4 or 5

- Baseline PASI category: <20 , ≥ 20
- Baseline BSA category: $<20\%$, $\geq 20\%$
- Previous psoriasis therapy subgroups:
 - Previous systemic therapy: never used, non-biologic only, biologic only, biologic and non-biologic.
 - Previous non-biologic systemic therapy: never used, ever used
 - Previous biologic therapy: never used, ever used
 - Where
 - Non-biologics include: methotrexate, cyclosporine, retinoids, corticosteroids, acitretin, fumaric acid derivatives, apremilast, PUVA, other
 - Biologics include: efalizumab, ustekinumab, infliximab, etanercept, alefacept, adalimumab, golimumab, certolizumab pegol, secukinumab, ixekizumab, other
- Concomitant topical steroid product use: yes, no.

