#### **Prior/Concomitant Therapy**

- [26] have received systemic nonbiologic psoriasis therapy (including, but not limited to, oral psoralen plus ultraviolet A light therapy [PUVA]; cyclosporine; corticosteroids; methotrexate; oral retinoids; apremilast; tofacitinib; mycophenolate mofetil; thioguanine; hydroxyurea; sirolimus; tacrolimus; azathioprine; fumaric acid derivatives; or 1, 25 dihydroxy vitamin D3 and analogues) or phototherapy (including either oral and topical PUVA light therapy, ultraviolet B, excimer laser, or self-treatment with tanning beds or therapeutic sunbathing) within 28 days prior to baseline
- [27] have received topical psoriasis treatment (including, but not limited to, corticosteroids [upper mid strength or lower potency topical steroids are permitted on the intertriginous areas and face], anthralin, calcipotriene, topical vitamin D derivatives, retinoids, tazarotene, pimecrolimus, tacrolimus, emollients and other nonprescription topical products containing urea, >3% salicylic acid, alpha- or beta-hydroxyl acids, or medicated shampoos [for example those that contain >3% salicylic acid, corticosteroids, coal tar, or vitamin D3 analogues]) within 14 days prior to baseline
- [28] have received anti-tumor necrosis factor (TNF) biologics or anti-IL-17 targeting biologics within 8 weeks prior to baseline

- [29] have previous exposure to any biologic therapy targeting IL-23 (including ustekinumab), either licensed or investigational (previous briakinumab use is permitted)
- [30] are unable or unwilling to avoid excessive sun exposure or use of tanning booths for at least 4 weeks prior to baseline and during the study

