#### **7.7. Concomitant Therapy**

All concomitant medication taken during the study must be recorded on the concomitant medication eCRF.

All subjects should maintain their usual medication regimens for concomitant conditions or diseases throughout the study unless those medications are specifically excluded in the protocol.

Subjects taking concomitant medications should be on stable dosages at the time of baseline and should remain at stable dosages throughout the study unless changes need to be made because of AEs. Additional systemic drugs are to be avoided during the study, unless required to treat AEs. Other medications may be allowed if they are approved by the sponsor or its designee.

Uses of nonlive (inactivated) vaccinations are allowed for all subjects. Use of live, attenuated vaccines is prohibited.

Concomitant therapies for treatment of psoriasis during the study are permitted only as outlined in [Table AMAF.4](#).

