 - BMI category: underweight (<18.5 kg/m²); normal (≥18.5 and <25 kg/m²); overweight (≥25 and <30 kg/m²); obese (≥30 and <40 kg/m²); extreme obese (≥40 kg/m²)
 - Alcohol use: never, current, former
 - Caffeine use: never, current, former
 - Tobacco use: never, current, former
 - Previous psoriasis therapy:
 - Previous systemic therapy: never used, non-biologic only, biologic only, biologic and non-biologic.
 - Previous non-biologic systemic therapy: never used, ever used
 - Previous biologic therapy: never used, ever used
 - Previous topical therapy: never used, topical prescription therapy, topical non-prescription therapy
 - Previous phototherapy (ultraviolet B [UVB] or PUVA): never used, ever used
- where
- Non-biologics include: methotrexate, cyclosporine, corticosteroids, acitretin, fumaric acid derivatives, apremilast, other
 - Biologics include: efalizumab, ustekinumab, infliximab, etanercept, alefacept, adalimumab, golimumab, certolizumab pegol, secukinumab, ixekizumab, other
- Duration of psoriasis (in years): Will be calculated using the date of psoriasis onset (as recorded on the Prespecified Medical History - Indication eCRF page) as follows:

$$\begin{aligned} & \textit{Duration of psoriasis (years)} \\ = & \frac{\textit{Date of informed consent} - \textit{Date of psoriasis onset}}{365.25} \end{aligned}$$

- Duration of psoriasis diagnosis (in years): Will be calculated using the date of psoriasis diagnosis (as recorded on the Prespecified Medical History - Indication eCRF page) as follows:

$$\begin{aligned} & \textit{Duration of psoriasis diagnosis (years)} \\ = & \frac{\textit{Date of informed consent} - \textit{Date of psoriasis diagnosis}}{365.25} \end{aligned}$$

- Baseline PASI score
- Baseline PASI category: $<20, \geq 20$
- Baseline PASI category: $<15, \geq 15$
- Baseline sPGA
- Baseline sPGA category: 0, 1, 2, 3, 4, 5
- Scalp psoriasis: yes, no (reported on Psoriasis Involvement eCRF form)
- Baseline PSSI score
- Baseline PSS score
- Baseline BSA (%)
- Baseline BSA category: $<20\%, \geq 20\%$
- Baseline DLQI total score
- Baseline DLQI total category: $<10, \geq 10$
- Baseline DLQI total category: $<5, \geq 5$
- Baseline DLQI total category: 0 or 1, >1
- Baseline SF-36 physical functioning score
- Baseline SF-36 role-physical score
- Baseline SF-36 role-emotional score
- Baseline SF-36 bodily pain score
- Baseline SF-36 vitality score
- Baseline SF-36 social functioning score
- Baseline SF-36 mental health score

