6.8. Concomitant Therapy

Medications will be classified into anatomical therapeutic chemical (ATC) drug classes using the latest version of the World Health Organization (WHO) drug dictionary.

Medication start and stop dates will be compared to the date of first dose of treatment in each treatment period to allow medications to be classified as Concomitant for each treatment period.

Prior medications are those medications that start and stop prior to the date of first dose of study treatment. Concomitant medications are those medications that start before, on or after the first day of study treatment of the defined treatment period and continue into the treatment period. Concomitant medications are assigned to the treatment period in which they are actually ongoing. For example, if a patient is receiving concomitant medication during the Induction Period but has a stop date during the Induction Period, the same medication would not be listed as a concomitant medication during the latter periods unless patient has a new start date.

Prior therapy (reported before randomization) and current concomitant therapy (reported after randomization) will be presented separately in frequency tables by drug name for all randomized patients.

The medical monitor for this study will identify the corticosteroids used by the patients from the list of concomitant medication collected during the course of this study. A summary table for the number and percent of patients using corticosteroids during the Induction Period will be presented by the treatment groups. This table will also include a summary on the quantity of corticosteroid used by the patients, if an imbalance is observed between dosing groups. Corticosteroid use may also be summarized in conjunction with efficacy.

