6.15.1. Efficacy Subgroup Analyses

Subgroup analyses will be conducted for the primary endpoint of proportion of patients achieving a PASI 90 at Week 16 (NRI) using the ITT population for the Induction Period. Subgroup analyses for the secondary efficacy endpoints, the proportion of patients achieving PASI 75, and PASI 100, will also be conducted at Week 16 (NRI) using the ITT population.

A logistic regression model with dosing regimen, subgroup, and the interaction of subgroup-by-dosing regimen, and previous biologic use (yes/no) included as factors will be used. The subgroup-by-dosing regimen interaction will be tested at the significance level of 0.10. Missing data will be imputed using NRI. If any treatment group within the subgroup has ≤ 5 subjects, only summaries of the efficacy data will be provided (that is, no inferential testing is planned).

Forest plots will be generated for efficacy subgroup analyses for pairwise comparisons between LY3074828 groups vs. placebo group.

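### The efficacy subgroup defined by concomitant topical steroid use can include use started after randomisation, so comparisons with placebo inside it are not protected by randomisation

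*SAP*

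**What the plan says.** SAP 6.15 gives one list of subgroups that will be analysed. Every entry is a demographic factor, region, a variable labelled as baseline, or a variable labelled as previous therapy, except the last: "Concomitant topical steroid product use: yes, no". It has no baseline qualifier, and the SAP does not say which period's use counts.

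SAP 6.8 gives the meaning of the word: "Concomitant medications are those medications that start before, on or after the first day of study treatment of the defined treatment period and continue into" that period. Use begun during induction therefore qualifies. The same section expects that steroid use might differ by arm, since the quantity used is to be summarised "if an imbalance is observed between dosing groups".

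SAP 6.15.1 states: "Subgroup analyses will be conducted for the primary endpoint of proportion of patients achieving a PASI 90 at Week 16 (NRI) using the ITT population". PASI 75 and PASI 100 are handled likewise. The model is a logistic regression with a subgroup-by-regimen interaction tested at 0.10, and forest plots show each dose against placebo. No caveat separates this subgroup from the others. If any treatment group within a subgroup has 5 or fewer subjects, only summaries are given. SAP 6.1.3 plans both odds ratios and treatment differences for binary endpoints. The scale of the forest plots is not stated.

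The subgroup list in Protocol 10.3.6.1 does not name this variable and leaves the detail to the SAP. Before baseline, exclusion [27] bars topical psoriasis treatment for 14 days, except that "upper mid strength or lower potency topical steroids are permitted on the intertriginous areas and face". During the study, "Concomitant therapies for treatment of psoriasis during the study are permitted only as outlined in" Table AMAF.4, whose content is redacted.

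**The concern.** A subgroup fixed before randomisation leaves comparable arms within each stratum. A subgroup formed by later behaviour need not. If subjects whose skin is not clearing reach for topical steroid more often, users on active drug are mainly its poor responders, whereas users on placebo resemble placebo subjects in general. The two are then not like for like, and the same holds for non-users. A reader of the forest plot could see a small benefit in users and a large one in non-users although the drug works equally in both. Any effect of the steroid itself on PASI would add a further distortion, which the illustration below leaves out.

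What is at stake is the reading of one supportive display in a Phase 2 study that Protocol 3.1 says will support the design of Phase 3.

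**Working it through.** **Inputs from SAP 5.2.** PASI 90 at Week 16 of 60% on LY3074828 and 3% on placebo, 50 per arm, two-sided Fisher's exact test at 0.05. **Assumptions, not in the documents:** all steroid use rates, the interim response rates and the correlations. Steroid is given no effect on PASI, and the true effect is the same for everyone.

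**The plan's own figure.** Exact enumeration of Fisher's test for 50 versus 50 at 60% and 3% gives power above 0.9999, so the stated figure of over 99% reproduces. The true difference is 60 - 3 = 57 points and the true odds ratio is (0.60/0.40)/(0.03/0.97) = 48.5.

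**Case A: use depends on Week 16 response, in the same way in both arms.** Let *p* be the response rate in an arm, *r* the use rate in responders and *s* the use rate in non-responders.

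- Response in users = *pr* / [*pr* + (1-*p*)*s*]
- Response in non-users = *p*(1-*r*) / [*p*(1-*r*) + (1-*p*)(1-*s*)]

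With *r* = 0.10 and *s* = 0.40:

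- Active: users 0.06/0.22 = 27.3%; non-users 0.54/0.78 = 69.2%
- Placebo: users 0.003/0.391 = 0.8%; non-users 0.027/0.609 = 4.4%
- Difference: users 26.5 points; non-users 64.8 points

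With *r* = 0.10 and *s* = 0.30:

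- Active: users 0.06/0.18 = 33.3%; non-users 0.54/0.82 = 65.9%
- Placebo: users 0.003/0.294 = 1.0%; non-users 0.027/0.706 = 3.8%
- Difference: users 32.3 points; non-users 62.0 points

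The odds of response in users are [*p*/(1-*p*)] × (*r*/*s*). The factor *r*/*s* is the same in both arms and cancels from the odds ratio; the corresponding factor cancels in non-users. For *s* = 0.40, users give (0.06/0.16)/(0.003/0.388) = 48.5 and non-users (0.54/0.24)/(0.027/0.582) = 48.5. Differences are distorted; the odds ratio is not.

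**Case B: use follows interim response.** Latent interim and Week 16 improvement are bivariate normal with correlation 0.5 or 0.8. Interim response is adequate in 70% on active and 5% on placebo. Use is 10% if adequate and 30% or 50% if inadequate. Results by simulation:

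| Correlation | Use if inadequate | Difference, users / non-users (points) | Odds ratio, users / non-users | Ratio of odds ratios |
|---|---|---|---|---|
| 0.5 | 30% | 48.5 / 58.5 | 40.0 / 49.0 | 0.82 |
| 0.5 | 50% | 44.5 / 60.2 | 35.5 / 48.1 | 0.74 |
| 0.8 | 30% | 42.3 / 59.6 | 41.7 / 47.6 | 0.87 |
| 0.8 | 50% | 35.3 / 62.3 | 35.5 / 44.6 | 0.80 |

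**Interaction test at nominal 0.10.** This was approximated by a Wald test with 0.5 added to each cell, for one active arm against placebo, in simulated trials where every cell had more than 5 subjects. It is not the SAP's Firth fit. On the log-odds scale the false-positive rate is about 3% when use is unrelated to response, 4-6% in case B and 7% in case A. All are below 10%, because 50 × 0.03 = 1.5 expected placebo responders make the test conservative. On the risk-difference scale, which is not the scale of the planned test, the rates are 16-47% in case B and 50-73% in case A.

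**Small-cell rule.** In case A with *s* = 0.30, expected users are 50 × 0.18 = 9 per active arm. The chance that at least one of the four arms has 5 or fewer users is about 25%. Over the use rates tried, including others not tabulated here, it runs from about 7% to 53%.

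**Control.** When use is unrelated to response, both strata show 57 points and an odds ratio of about 48.5.

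**The case against.** A reader might infer that the planned interaction test is itself biased and will readily report a false difference in effect. The documents do not support that. The test is a logistic one. In case A its target, the ratio of odds ratios, is exactly 1. In case B it departs from 1, but the false-positive rate stays below nominal at this sample size. The 5-or-fewer rule may also stop the test from being run.

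A reader might also take it as established that steroid use depends on response. No passage says so, and the visible rules limit such use: Protocol 7.7 restricts psoriasis therapy to Table AMAF.4 and asks for stable concomitant doses, and Protocol 8.2 has a subject who needs another effective agent leave the study before it is started. Some users may simply be continuing the facial or intertriginous steroid that exclusion [27] allows. The use rates above are therefore assumptions, and the redacted table prevents better ones.

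This is one line in a supportive list, and nothing in the documents ties it to Phase 3 rules on concomitant therapy.

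All of this stands, and it limits the size of the point. It does not remove the structural weakness: a variable that can be determined after randomisation is analysed exactly like a baseline factor, and treatment differences, the scale most exposed, are a planned output for binary endpoints.

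**Conclusion.** The point holds as a minor one, with moderate confidence. Treatment comparisons within strata of concomitant topical steroid use are not protected by randomisation. If use tracks response, the risk differences in users and non-users can move well away from a common true value of 57 points: to about 27-32 and 62-65 in case A, and about 35-49 and 59-62 in case B. On the odds-ratio scale the distortion runs from none to a ratio of 0.74-0.87, with no false-positive rate above the nominal level for the interaction test under the approximation used. These figures rest on assumed use rates, the SAP's 60% and 3%, no effect of steroid on PASI and, in case B, one assumed model of interim response. They show what could happen and do not estimate what did. The primary ITT comparison of PASI 90 at Week 16, and its power, are untouched.

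**What to change.** In SAP 6.15, either:

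- define the subgroup as topical steroid use at or before baseline (yes/no); concomitant medication is recorded at Visits 1 and 2 in the Schedule of Activities, so no new visit or procedure is needed; or
- keep the variable out of the interaction tests and forest plots.

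In both cases, report on-treatment steroid use by arm descriptively. SAP 6.8 already plans an Induction Period table of corticosteroid users by treatment group; showing topical use separately there would be enough.

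The baseline item in SAP 6.6, "Previous topical therapy: never used, topical prescription therapy, topical non-prescription therapy", is not a substitute. It records history and does not identify steroids or use at baseline.

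The cost is about one line of text. The drawbacks are that the baseline-user group may be small, so the 5-or-fewer rule may still leave only summaries, and that the question about on-treatment use is answered only descriptively. Protocol 10.3.6.1 does not name this subgroup, so neither option conflicts with it.

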6.15.1. Efficacy Subgroup Analyses

Subgroup analyses will be conducted for the primary endpoint of proportion of patients achieving a PASI 90 at Week 16 (NRI) using the ITT population for the Induction Period. Subgroup analyses for the secondary efficacy endpoints, the proportion of patients achieving PASI 75, and PASI 100, will also be conducted at Week 16 (NRI) using the ITT population.

A logistic regression model with dosing regimen, subgroup, and the interaction of subgroup-by-dosing regimen, and previous biologic use (yes/no) included as factors will be used. The subgroup-by-dosing regimen interaction will be tested at the significance level of 0.10. Missing data will be imputed using NRI. If any treatment group within the subgroup has ≤ 5 subjects, only summaries of the efficacy data will be provided (that is, no inferential testing is planned).

Forest plots will be generated for efficacy subgroup analyses for pairwise comparisons between LY3074828 groups vs. placebo group.

6.15.2. Safety Subgroup Analyses

Safety subgroup analysis for common TEAEs may be summarized by treatment and overall, for the safety population during the Induction and Maintenance Periods.

6.16. Protocol Violations

Review of all major and minor protocol violations will be performed on an ongoing basis during the conduct of the study. All protocol exemptions/violations identified from the following sources will be tracked:

- During clinical monitoring visits

- During data validation process.

No patient will be excluded from the ITT population due to any protocol violations.

There is no Per-Protocol Population in this plan.

All protocol exemptions and violations that require medical review will be listed.

6.17. Interim Analyses and Data Monitoring

Two interim analyses will be conducted according to the specifications set forth in the protocol.

- Interim Analysis 1 (Primary Analysis): Once all patients complete the 16-week Induction Period or discontinue prior to Week 16
- Interim Analysis 2 (Post-Primary Interim Analysis): Once all patients on PRN dosing complete 16 weeks in the Maintenance Period or discontinue during the Maintenance Period.

This is a double-blind study during the Induction Period. Baseline dose cohort assignment will remain blinded throughout the study; however, during the Maintenance Period, dosing strategy (PRN or Q8W) will be open label. To preserve the blinding of the study, a minimum number of Lilly personnel will see the randomization table and treatment assignments before the study is complete.

To minimize any bias being introduced into the analysis of the study results, the SAP and PK/PD analysis plan will be finalized and approved before the efficacy interim analysis begins. Information that may unblind the study during the analyses will not be reported to study sites or the blinded study team until the study has been unblinded.

The interim analyses will be conducted for internal decision for future development. Interim analyses will not impact the current study design or implementation. The study may not be stopped for positive efficacy. Hence, there will be no alpha adjustment for the interim analysis.

Ongoing monitoring of safety data (including AEs, SAEs, and selected laboratory measurements) will be continued throughout the study using blinded data. Reviewing details are specified in the TLSR plan or a separate document.

